## Modified Intent-to-Treat (mITT) Population

The mITT Population will be a subset of the ITT Population and excludes subjects with duplicate enrollments either within BBI-4000-CL-301 or across BBI-4000-CL-301 and BBI-BL-4000-CL-302 (see Section 3.3). All other subjects will be analyzed according to the treatment group to which they were randomized, regardless of post-randomization protocol deviations, including no treatment or wrong treatment received.

Version: 2.0 Page 17 of 74

## 5. STUDY SUBJECTS

## 5.1 Disposition of Subjects

Subject disposition will be summarized by treatment group for Safety, ITT, mITT, and PP populations separately. Summaries will include the number and percentage of subjects completing treatment, completing the study, and discontinuing the study early by the primary reason for discontinuation. The number and percentage of subjects excluded and reason for exclusion will be included in the PP population disposition table.

All subject disposition data will be listed by clinical site.

### 5.2 Protocol Violations

Major protocol violations will be summarized by treatment group for the Safety Population. Major protocol violations may include, but will not be limited to the following:

- Not meeting eligibility criteria;
- Randomization error;
- Received no protocol treatment or wrong treatment;
- Non-compliance with study drug dosing;
- On-study administration of a prohibited medication;
- Unauthorized changes to protocol procedure that could potentially affect subject safety or are a flagrant deviation of protocol defined procedures.

All major protocol violations will be determined and appropriately categorized prior to database lock and prior to breaking the blind of the treatment group assignments. The number and percentage of subjects with any major protocol violations as well as the number and percentage of subjects with violations within each category will presented. A per subject listing will be provided for all protocol violations, major or minor, for the Safety Population.

Version: 2.0 Page 18 of 74

#### 6. DEMOGRAPHIC AND OTHER BASELINE CHARACTERISTICS

Demographic variables including age, sex, ethnicity, race, and predominant race, will be summarized by treatment group for the Safety, ITT, mITT, and PP Populations.

Age will be summarized using descriptive statistics. Age will also be categorized into 9-12, 13-16, 17-30, and  $\geq$  31 years of age. Age groups, sex, ethnicity, race, and predominant race will be summarized with the number and percentage of subjects in each parameter category. If more than one race is reported, subjects will be counted in each relevant category.

Baseline characteristics include medical history, height, weight, time since onset of axillary hyperhidrosis symptoms, and body mass index (BMI). Medical history will be summarized for the Safety Population. Other baseline characteristics will be summarized for the Safety, ITT, mITT, and PP Populations by treatment group.

Height, weight, BMI, and time since onset of axillary hyperhidrosis symptoms at baseline will be summarized using descriptive statistics. BMI will be calculated as: weight (kg) / (height (cm) / 100). If height is entered in inches, height is converted to cm by Height (cm) = 2.54 \*Height (inches). If weight is entered in lbs, weight is converted to kg by Weight (kg) = Weight (lbs) / 2.2046. Time since onset of axillary hyperhidrosis symptoms will be reported in months and calculated by dividing the duration in days by (365.25 / 12). Duration in days will be calculated as (date of informed consent – start date of axillary hyperhidrosis symptoms + 1).

Medical history events will be coded to system organ class using the most current version of MedDRA. Frequency counts and percentages will be used to summarize subjects reporting abnormal medical history by system organ class. Subjects reporting more than one event for a given system organ class will be counted only once for that system organ class. All demography, baseline characteristics, and medical history data collected will be presented in listings.

Version: 2.0 Page 19 of 74

#### 7. MEASUREMENTS OF STUDY TREATMENT EXPOSURE

Extent of study treatment exposure will be summarized for the Safety Population by treatment group. The duration of exposure will be presented in days and calculated as the date of last dose of study drug minus the date of first dose of study drug, plus one.

Study treatment exposure will be calculated for each subject by taking into account whether a subject took all doses of study drug as instructed through dosing deviations, including dose interruptions/modifications for AEs/tolerability, collected on the dosing page of the eCRF. For each dosing entry, study treatment exposure will be determined as the total number of doses received divided by the number of expected doses, multiplied by 100. As the standard dosing regimen is for study drug to be applied 1 time daily per axilla, the expected number of doses will be the number of days between the date of last dose of study drug minus the date of first dose of study drug, plus one, times two. The number of doses received will be the number of days between the date of last dose of study drug minus the date of first dose of study drug, plus one, multiplied by 2, minus the number of missed doses recorded on the dosing page of the eCRF.

Study treatment exposure will be calculated at the subject-level (i.e. across all dosing entries) and will be summarized using descriptive statistics.

Drug (pump) dispensation will be provided in a listing, to include total drug delivered per subject. Each pump will be primed, then weighed, prior to dispensing pumps to subjects. Each pump will be weighed upon return. Total drug delivered will be calculated as the total weight of all pumps dispensed minus the total weight of all returned pumps.

Version: 2.0 Page 20 of 74

#### 8. EFFICACY EVALUATION

## 8.1 Efficacy Endpoints

The following assessment measures will be conducted to evaluate the efficacy of BBI-4000:

- Hyperhidrosis Disease Severity Measurement-Axillary (HDSM-Ax) as measured by the subject (for subjects ≥12 years of age)
- Hyperhidrosis Disease Severity Measurement-Axillary, Child (HDSM-Ax, Child) as measured by the subject (for subjects ≥9 to <12 years of age)
- Gravimetrically measured sweat production (GSP)
- Dermatology Life Quality Index (DLQI) axilla, as measured by the subject (for subjects ≥17 years of age)
- Patient Global Impression Scales\*; Severity (PGI-S\*\*) and Change (PGI-C†)
  - \* These questions will be included in the HDSM-Ax questionnaires
  - \*\* Administered as Question #6 of HDSM-Ax at each assessment
  - † Administered as Question #7 of HDSM-Ax at the Day 43 visit only

### 8.1.1 Definitions

For the purposes of analysis, Baseline and End of Treatment (EOT) definitions for the two primary efficacy assessment measures, HDSM-Ax and Gravimetric Sweat Production (GSP), as well as the other efficacy parameters of interest, are defined below.

#### **HDSM-Ax**

The HDSM-Ax-7 scale will be defined as the mean of the items in section No. 1 and questions 2a. through 2e. of the HDSM-Ax (7 sub-items in total). This will apply to both the  $\geq$  12 years of age scale and the 9-11 year old scale. The mean will be derived by taking the sum of 7 item scores and dividing it by 7. Subjects must answer all of the 7 sub-items for the HDSM-Ax-7 score to be evaluable/non-missing.

The HDSM-Ax-11 scale will be defined as mean of the items in sections No. 1, 2, and 3 of the HDSM-Ax (11 sub-items in total). This will apply to both the  $\geq$  12 years of age scale and the 9-11 year old scale. The mean will be derived by taking the total score and dividing by the number of questions answered. Subjects must answer at least 6 of the 11 sub-items for the HDSM-Ax-11 score to be evaluable/non-missing.

Baseline and End of therapy HDSM-Ax values are defined as follows:

- Baseline = Visit 4 (Day 1) assessment
- EOT = Visit 12 (Day 43) assessment

Version: 2.0 Page 21 of 74

### **GSP** (both axillae combined total)

Baseline and End of therapy values are defined as follows:

- Baseline = the median of GSP1, GSP2, and GSP3 measurements obtained on Visit 2, Visit 3, and Visit 4, respectively
- EOT = the median of GSP4, GSP5, and GSP6 measurements obtained on Visit 10, Visit 11, and Visit 12, respectively

Note that at each timepoint, GSP will be defined as the sum of both axillae measurements. If one axilla value is missing at a timepoint, then the non-missing observed value will be multiplied by 2. The values for baseline or EOT will not be regarded as missing as long as the measurement is available at least for one of the three timepoints. Negative GSP values will be treated as missing.

#### DLQI (axilla)

The DLQI total score is calculated by summing answers to questions 1 through 10, including both parts of Question 7. The answer to each individual question is scored as follows':

```
"Very much" = 3

"A lot" = 2

"A little" = 1

"Not at all" = 0

"Not relevant" = 0

Question 7, "prevented work or studying" = 3
```

All questions must be answered at the first DLQI assessment. Subsequent DLQI assessments missing an answer for a single question will be scored 0 for that question and totaled. Question 7 will be considered answered if Part 2 is answered even if No is not checked for Part 1. Subjects missing data for more than one question will have the instrument dropped for that visit.

Baseline and End of therapy values are defined as follows.

- Baseline = Visit 4 (Day 1) assessment
- EOT = Visit 12 (Day 43) assessment

#### Patient Global Impression Scales; Severity (PGI-S) and Change (PGI-C)

PGI-S will be defined as Question #6 of the HDSM-Ax at each assessment. PGI-C will be defined as Question #7 of the HDSM-Ax at the Day 43 visit only.

Version: 2.0 Page 22 of 74

# 8.1.2 Co-Primary Efficacy Endpoints

The following co-primary efficacy endpoints will be analyzed to assess the efficacy of sofpironium bromide gel, 15%:

- The proportion of subjects achieving at least a 2-point improvement in the HDSM-Ax-7 scale score from baseline to EOT (responders).
- The change in GSP from baseline to EOT.

Note that the analysis of the HDSM-Ax co-primary efficacy endpoint will be conducted using 7 of the 11 items on the HDSM-Ax scale. More specifically, the mean of the 2 items in section 1 and the first 5 items in section 2 (7 sub-items in total) will be used. The mean will be derived by taking the sum of 7 item scores and dividing it by 7. For each of the HDSM-Ax sub-items, missing values at EOT will be imputed per Section 8.2.1.1 and Appendix 18.2. HDSM-Ax-7 at EOT will be derived from the imputed values.

## 8.1.3 Secondary Efficacy Endpoints

The following secondary efficacy endpoints will be analyzed:

- The proportion of subjects achieving at least a 1-point improvement in the HDSM-Ax-7 scale score from baseline to EOT.
- The proportion of subjects achieving at least a 2-point improvement in the HDSM-Ax-7 scale score from baseline to EOT and achieving at least a 70% reduction in GSP from baseline to EOT.
- The proportion of subjects achieving at least a 1-point improvement in the HDSM-Ax-7 scale score from baseline to EOT and achieving at least a 50% reduction in GSP from baseline to EOT.

### 8.1.4 Exploratory Efficacy Endpoints

Exploratory efficacy endpoints to be analyzed include the following:

- The proportion of subjects achieving at least a 1-point improvement in the HDSM-Ax-7 scale score from baseline to Days 8, 15, 22, 29, 36, 41, 42, 43 (EOT), and 57.
- The proportion of subjects achieving at least a 1-point improvement in the HDSM-Ax 11-Item (HDSM-Ax-11) scale score from baseline to Days 8, 15, 22, 29, 36, 41, 42, 43 (EOT), and 57.
- The proportion of subjects achieving at least a 2-point improvement in the HDSM-Ax-7 scale score from baseline to Days 8, 15, 22, 29, 36, 41, 42, 43 (EOT), and 57.
- The proportion of subjects achieving at least a 2-point improvement in the HDSM-Ax-11 scale score from baseline to Days 8, 15, 22, 29, 36, 41, 42, 43 (EOT), and 57.

Version: 2.0 Page 23 of 74

- The proportion of subjects achieving at least a 1-point improvement in the HDSM-Ax Question 4 score from baseline to Days 8, 15, 22, 29, 36, 41, 42, 43 (EOT), and 57.
- The proportion of subjects achieving at least a 2-point improvement in the HDSM-Ax Question 4 score from baseline to Days 8, 15, 22, 29, 36, 41, 42, 43 (EOT), and 57.
- The proportion of subjects achieving at least a 1-point improvement in the HDSM-Ax Question 5 score from baseline to Days 8, 15, 22, 29, 36, 41, 42, 43 (EOT), and 57.
- The proportion of subjects achieving at least a 2-point improvement in the HDSM-Ax Question 5 score from baseline to Days 8, 15, 22, 29, 36, 41, 42, 43 (EOT), and 57.
- Change in PGI-S from baseline to Days 8, 15, 22, 29, 36, 41, 42, 43, and 57.
- PGI-C score on Day 43.
- The proportion of subjects achieving at least a 2-point improvement in the HDSM-Ax-11 scale score from baseline to EOT and achieving at least a 70% reduction in GSP from baseline to EOT.
- The proportion of subjects achieving at least a 1-point improvement in the HDSM-Ax-11 scale score from baseline to EOT and achieving at least a 50% reduction in GSP from baseline to EOT.
- The proportion of subjects achieving at least a 2-point improvement in the HDSM-Ax-7 scale score and achieving at least a 70% reduction in GSP from baseline to Days 8, 15, 22, 29, 36, 41, 42, 43, EOT, and Day 57.
- The proportion of subjects achieving at least a 2-point improvement in the HDSM-Ax-11 scale score and achieving at least a 70% reduction in GSP from baseline to Days 8, 15, 22, 29, 36, 41, 42, 43, EOT, and Day 57.
- The proportion of subjects achieving at least a 1-point improvement in the HDSM-Ax-7 scale score and achieving at least a 50% reduction in GSP from baseline to Days 8, 15, 22, 29, 36, 41, 42, 43, EOT, and Day 57.
- The proportion of subjects achieving at least a 1-point improvement in the HDSM-Ax-11 scale score and achieving at least a 50% reduction in GSP from baseline to Days 8, 15, 22, 29, 36, 41, 42, 43, EOT, and Day 57.
- Change in HDSM-Ax-7 scale score from baseline to Days 8, 15, 22, 29, 36, 41, 42, 43 (EOT), and 57 as a continuous measure.
- Change in HDSM-Ax-11 scale score from baseline to Days 8, 15, 22, 29, 36, 41, 42, 43 (EOT), and 57 as a continuous measure.
- The proportion of subjects achieving at least a 70% reduction in GSP from baseline to Days 8, 15, 22, 29, 36, 41, 42, 43, EOT, and Day 57.
- The proportion of subjects achieving at least a 50% reduction in GSP from baseline to Days 8, 15, 22, 29, 36, 41, 42, 43, EOT, and Day 57.

Version: 2.0 Page 24 of 74

- The rank-based GSP change from baseline to Days 8, 15, 22, 29, 36, 41, 42, 43, EOT, and Day 57.
- The absolute GSP change from baseline to Days 8, 15, 22, 29, 36, 41, 42, 43, EOT, and Day 57.
- The percent change from baseline in GSP from baseline to Days 8, 15, 22, 29, 36, 41, 42, 43, EOT, and Day 57.
- The change in the DLQI (axilla) from baseline to Day 15 and Day 43 (EOT).

# 8.2 Overview of Efficacy Analysis Issues

### 8.2.1 Handling of Dropouts or Missing Data

# 8.2.1.1 Multiple Imputations for Missing Data on Co-Primary Endpoints

For both HDSM-Ax-7 (diagram in Appendix 18.2) and GSP (diagram in Appendix 18.3), multiple imputations for missing EOT values in the vehicle group will be performed assuming Missing at Random (MAR). For the sofpironium bromide gel, 15% group, multiple imputations using a control-based imputations (CBI) model will be employed as the primary imputation method to handle missing EOT data. This approach will adopt a missing not at random (MNAR) assumption. It assumes that, due to discontinuing treatment, a subject who has been benefiting from sofpironium bromide gel, 15%, would maintain its benefit up to the last known efficacy endpoint value and from then on behave like a subject on vehicle. That is, the subject's efficacy trajectory after dropping out would be similar to that of a subject on vehicle with like subject characteristics and endpoint history up to the last observed visit for the sofpironium bromide gel, 15%, subject.

Twenty imputed datasets will be generated for each of the co-primary efficacy endpoints. The same co-primary analysis models (Section 8.3) will be applied to the multiple imputed datasets and the results combined via Rubin's rules (Rubin, 1976).

HDSM-Ax individual missing items scores will be imputed. If the individual item score is missing at Visit 12, but non-missing at either Visits 10 and or/11, then the closest (in time) non-missing score will be carried forward. If the individual item score is missing at all three visits of Visits 10, 11, and 12, then individual item scores will be imputed for all three visits. The mean will be derived from the imputed values. Further details are provided in Section 8.3.1 below.

GSP at EOT will only be multiply imputed if both the right and left axilla weights are missing at all three visits of Visits 10, 11, and 12. Further details are provided in Section 8.3.2 below.

Version: 2.0 Page 25 of 74

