#### 2 STUDY DESIGN

This is a multicenter, randomized, double-blinded, vehicle-controlled, Phase 3 study to evaluate the safety and efficacy of topically applied sofpironium bromide gel, 15% in subjects with primary axillary hyperhidrosis.

Approximately 350 subjects, at up to approximately 45 clinical sites in the US, will be enrolled to obtain approximately 300 evaluable subjects at the end of study.

Subjects will be randomized 1:1 to receive sofpironium bromide gel, 15% or vehicle gel (175 subjects dosed with 15% gel and 175 subjects dosed with vehicle gel). Subjects will apply the investigational product once daily at bedtime to their axillae for 42 consecutive days.

Patient-reported outcomes HDSM-Ax, Patient Global Impression of Severity (PGI-S), Patient Global Impression of Change (PGI-C; EOT only), and DLQI, as well as Investigator-reported GSP, will be recorded during the study at predefined time points. Vital signs and local tolerability assessments will be collected at Visits 4 through 9 and Visits 12 (EOT) and 13. Adverse events will be collected at each post-Screening visit. Blood and urine samples will be collected and analyzed at Screening and Visit 12/EOT for routine hematology, chemistry, and urinalysis parameters. Additionally, a urine pregnancy test (UPT) for females of child-bearing potential (FOCBP) will be collected and analyzed at Visits 1, 4, 8, and 12.

A total of 13 scheduled visits will take place over approximately 11 to 15 weeks, depending on when the Baseline Visit (treatment) is scheduled after the three (3) screening period visits: initial screening, GSP1, and GSP2. See Section 7.1 for an events table of this study.

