## 10.5 Sample Size

Sample size estimation was performed for the co-primary efficacy endpoints based on the results of a Phase 2b study (BBI-4000-CL-203):

- HDSM-Ax-7 responder analysis: 2-point improvement response rates of 29.8% and 53.7% were assumed for the vehicle and sofpironium bromide gel, 15% arms, respectively. The power is 0.95 with 116 subjects per arm and a total of 232 subjects.
- GSP: using rank-transformed GSP data for change from baseline to EOT, a difference of 16.6 in mean ranks between the vehicle and sofpironium bromide gel, 15% arms, with a pooled standard deviation of approximately 39.5, was used for this purpose. Normal approximation yielded a sample size estimate of 296 subjects for the study, 148 each arm, in order to achieve 0.95 power for the GSP co-primary endpoint.

A chi-square test for the HDSM-Ax-7 endpoint and a two-sample t-test for the GSP endpoint were used to estimate the above sample size and power for each endpoint. With approximately 300 evaluable subjects, the overall study power to demonstrate a statistically significant treatment effect (two-sided p < 0.05) for both coprimary efficacy endpoints simultaneously is greater than 0.90 (with greater than 0.95 power for each of HDSM-Ax-7 and GSP).

Assuming missing data from approximately 15% of subjects, a total of 350 subjects will be targeted for enrollment.

Additionally, sample size estimation was also performed using non-rank-transformed GSP data. An expected mean treatment difference of 73 mg with a pooled standard deviation of approximately 170 was used for this purpose. This yielded a reduced sample size estimate compared with the target of 300 subjects completing the coprimary efficacy assessments in order to achieve 0.95 power for GSP, further indicating that our sample size estimations are conservative.

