## 8.3 Analysis Methods

With the exclusion of Section 8.3.7 Exploratory Efficacy Analyses, all other Section 8.3 analyses will be repeated for the mITT population.

The primary efficacy analysis will be performed on the ITT population with missing values imputed. The co-primary efficacy outcomes are:

- The proportion of subjects achieving at least a 2-point improvement in the HDSM-Ax-7 scale score from baseline to EOT in the sofpironium bromide gel, 15% group versus vehicle; and
- The change in GSP from baseline to EOT in the sofpironium bromide gel, 15% group versus vehicle.

Both comparisons will be conducted using two-sided tests at an alpha=0.05 level. Both endpoints will need to demonstrate a statistically significant positive result in favor of sofpironium bromide gel, 15% for the study to be considered successful.

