# 8.3.5.4 Sensitivity Analysis 4: HDSM-Ax-7 and GSP, Tipping Point Analysis

A tipping point analysis will be conducted to investigate what type of missing data would cause a positive between-arm comparison of the outcomes of the co-primary efficacy endpoints to be non-significant. These analyses will be conducted separately for the HDSM-Ax-7 and GSP co-primary endpoints.

For the GSP co-primary endpoint, missing data in the vehicle arm will be assumed to be MAR, while missing data from the sofpironium bromide gel, 15% arm will be imputed assuming that subjects with missing data have missing GSP data that are worse by a prespecified  $\Delta$  compared to similar subjects with observed data. Missing values will be multiply imputed via this method with increasing  $\Delta$  values. A  $\Delta$  increment of 5 mg will be used for this study. The GSP co-primary efficacy outcome analysis methodology will be applied to the imputed datasets and repeated until statistical significance no longer holds. The tipping point at which the results are no longer significant will be identified and the results will be summarized graphically.

For the HDSM-Ax-7 co-primary endpoint, identical imputation methodology to that described above for the GSP will be applied to the HDSM-Ax-7 total scores, and the resulting values will be dichotomized into responders using the 2-point improvement criteria. A  $\Delta$  increment of 0.5 (in a 0-4 scale) will be used for this study. The HDSM-Ax-7 co-primary efficacy outcome analysis methodology will be applied to the imputed datasets and repeated until statistical significance no longer holds. The tipping point at which the results are no longer significant will be identified and the results will be summarized graphically.

Version: 2.0 Page 35 of 74

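### Twenty imputations with no stated seed leave a co-primary p-value near 0.05, and the GSP tipping point, partly dependent on the random seed; raising the number is a cheap improvement

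*SAP*

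**What the plan says.** SAP 8.2.1.1 fixes the number of imputations: "Twenty imputed datasets will be generated for each of the co-primary efficacy endpoints". Results are pooled by Rubin's rules. SAP 8.3.1 and 8.3.2 refer again to the 20 imputations when they describe the site poolability tests.

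On the decision rule, SAP 8.3 states: "Both comparisons will be conducted using two-sided tests at an alpha=0.05 level". Both must succeed, and under SAP 8.2.4 the three secondary endpoints are tested only if they do.

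On the amount of missing data, Protocol 10.5 states: "Assuming missing data from approximately 15% of subjects, a total of 350 subjects will be targeted for enrollment". SAP 8.2.1.1 narrows what is multiply imputed: "GSP at EOT will only be multiply imputed if both the right and left axilla weights are missing at all three visits". The three meant are the final GSP visits, 10 to 12. HDSM-Ax items missing at Visit 12 are first filled from Visit 10 or 11.

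For the GSP tipping-point analysis, SAP 8.3.5.4 says that a Δ "increment of 5 mg will be used for this study" and that the co-primary analysis is "repeated until statistical significance no longer holds". It gives no number of imputations of its own.

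The readable text states no seed, no Monte Carlo error limit and no rule for raising the number. The imputation flow charts (SAP Appendices 18.2 and 18.3) are figures that could not be read, so they may hold such details.

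**The concern.** Twenty imputations are ample for efficiency: the pooled standard error hardly changes with more. They are less adequate for a reproducible p-value, because the pooled estimate still carries random error from the imputation draws. Far from 0.05 that error is harmless. Close to 0.05, two statisticians who follow the plan correctly with different seeds can reach different verdicts on a co-primary endpoint, and so on whether the secondary tests are opened.

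The tipping-point analysis is exposed by construction. It moves Δ until p reaches 0.05, so it always stops where the seed matters most.

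**Working it through.** **Inputs from the documents.** 20 imputations; two-sided 0.05; about 15% missing; 175 per arm (Protocol 2); GSP difference 73 mg with SD 170, or 16.6 ranks with SD 39.5; HDSM-Ax-7 response 29.8% and 53.7%; 5 mg step.

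**Assumptions.** Fraction of missing information (FMI) 0.05 to 0.15; correlation of an earlier visit with end of treatment 0, 0.5 or 0.7; 8% as an alternative missing share; 50 mg as an alternative effect.

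**1. The plan's own figures.** For GSP ranks, n per arm = 2 × (1.960 + 1.645)² × 39.5² / 16.6², which rounds up to 148, as stated. For HDSM-Ax-7 the stated 116 is reproduced with a continuity correction (108 without). At 150 per arm, power is 0.953 for GSP ranks and 0.989 for HDSM-Ax-7. The readable text states no Monte Carlo error to reproduce.

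**2. Seed noise in z.** SD ≈ √(FMI/m). With m = 20:
- FMI 0.15: √(0.15/20) = 0.087
- FMI 0.10: 0.071
- FMI 0.05: 0.050

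For a long-run p of 0.05, the 95% range over seeds is 0.033–0.073, 0.036–0.069 and 0.040–0.063 respectively.

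**3. Chance of crossing 0.05.** A long-run p of 0.04 has z = 2.054, which is 0.094 above 1.960. The chance of p ≥ 0.05 is 1 − Φ(0.094/SD): about 14%, 9% and 3% for the three values of FMI.

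In simulations that varied only the seed:

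| Endpoint, missing share | Long-run p | Seeds with p ≥ 0.05, m = 20 |
|---|---|---|
| GSP, 15% (correlation 0 / 0.5 / 0.7) | 0.04 | 17% / 11% / 8% |
| GSP, 15% (same) | 0.03 | 2.4% / 0.2% / 0.1% |
| GSP, 8% | 0.04 | 3 to 10% |
| HDSM-Ax-7, 15% | 0.047 | 43% |
| HDSM-Ax-7, 15% | 0.037 | 10% |
| HDSM-Ax-7, 15% | 0.029 | 0.7% |

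With m = 200, a long-run GSP p of 0.04 crossed 0.05 in none of 300 seeds.

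**4. Averaged over the planned design.** The chance that 20 imputations give a different verdict from infinitely many is about φ(1.96 − δ) × 0.798 × SD, where δ is the expected z. For seed SD of 0.05 to 0.09:
- GSP, δ = 16.6 / (39.5 × √(2/150)) = 3.64: φ = 0.097, giving about 0.4 to 0.7%.
- HDSM-Ax-7, δ = 4.25 (power 0.989): φ = 0.029, giving about 0.1 to 0.2%.

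In one simulated trial at the planned 73 mg effect, none of 1000 seeds lost significance (largest p 0.012).

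**5. GSP tipping point, continuous data, m = 20.** The SE of the difference is 170 × √(2/148.75) = 19.7 mg, where 148.75 = 0.85 × 175. Seed noise in the difference is 0.087 × 19.7 = 1.7 mg. One step shifts the difference by 0.15 × 5 = 0.75 mg, or 0.038 on the z scale. The noise is therefore 1.7/0.75 ≈ 2.3 steps, about 11 mg of Δ.

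Simulated tipping points at 15% missing:

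| Effect, correlation | Median | SD, m = 20 | 95% seed range, m = 20 | SD, m = 200 |
|---|---|---|---|---|
| 73 mg, 0 | 220 mg | 12.7 | 195–240 | 4.6 |
| 73 mg, 0.7 | 285 mg | 7.9 | 270–300 | 3.0 |
| 50 mg, 0 | 75 mg | 13.3 | 50–95 | 4.6 |
| 50 mg, 0.7 | 145 mg | 8.3 | 130–160 | 3.3 |

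In the first row, 200 seeds gave 14 different tipping points, and the commonest came from 18% of seeds. Ranked data were somewhat noisier: SD about 9 to 18 mg at 20 and 4 to 7 mg at 200, over both missing shares. With ranked data, 8% missing and the 73 mg effect, no tipping point was reached up to 3000 mg.

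**6. Imputations for an SD of half a step (2.5 mg).** About 410 at 15% missing without help from earlier visits, about 210 if those visits explain half the variance, and about 1100 at 5% missing.

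**The case against.** Several points on the other side stand.

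- **The imputed share may well be below 15%.** GSP is multiply imputed only when all three final visits are missing, HDSM-Ax items are carried from Visits 10 and 11, and Protocol 7.4 asks early discontinuers to complete the Visit 12 evaluations. SAP 8.2.1.1 also conditions on endpoint history, which reduces the noise.
- **Flip rates depend on the p-value chosen.** At FMI 0.15, a long-run p of 0.045 gives about 30%. A reader might infer that a third of runs of this trial would disagree. That figure describes only a result already very close to the threshold; step 4 gives the rate for the planned trial.
- **A reader might infer inflated type I error or bias.** The documents do not support this. Rubin's total variance already includes a term for the finite number of imputations.
- **A reader might take 5 mg as a promised resolution.** SAP 8.3.5.4 states only a search increment. It sets no decision threshold, and a shift of two or three steps would rarely change the reading of a tipping point of 220 mg or more.
- **That 20 applies in 8.3.5.4 is an inference.** It rests on the instruction there to use the co-primary methodology.
- **The seed may be recorded elsewhere**, in the flow charts or the statistical validation plan mentioned in SAP 3.1.

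These points limit the size of the concern. They do not remove it: the noise near 0.05 appears in every scenario tried and is cheap to reduce.

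**Conclusion.** This is a cheap improvement, not a flaw that threatens the trial's conclusion. With 20 imputations, a co-primary result whose long-run p is about 0.03 to 0.07 can change sides of 0.05 with the seed, in about 3 to 17% of seeds at p = 0.04. At the planned effects the two co-primary rates sum to under about 1% of trials. The documents state no power for the secondary endpoints, so that reassurance does not carry over to them.

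If 20 also governs the tipping-point analysis, the GSP tipping point has a seed SD of about 8 to 14 mg on continuous data, when a tipping point exists. That matters mainly when the tipping value is small, as in the 50–95 mg spread around 75 mg.

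Only the 15% comes from the documents; FMI, visit correlations and the 8% share are assumptions. The simulations left out baseline and analysis center, used one earlier visit and treated HDSM-Ax-7 response as a binary draw. Better predictors would reduce the noise but not remove it.

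**What to change.** - **SAP 8.2.1.1:** set at least 200 imputed datasets per co-primary endpoint and state the seed. The seed makes a rerun repeatable; the larger number makes the choice of seed matter little. Fix both before unblinding.
- **SAP 8.3.5.4:** state the same number and reuse the same base imputations at every Δ, so that the first loss of significance reflects Δ and not a fresh draw.
- **SAP 8.3.1 and 8.3.2:** change the references to 20 imputations, two in each section, to match.

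At 200, the tipping-point SD falls to about 3 to 5 mg on continuous data, within about one step. If half a step is wanted at 15% missing, about 400 are needed.

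The estimand, models and alpha do not change. The cost is run time, plus slightly more chances of triggering the non-convergence rule in SAP 8.2.2, which re-pools centers to at least 35 subjects, then 70, and finally drops the center term.
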